8.11. Occupational Exposure

An occupational exposure occurs when during the performance of job duties, a person (whether a healthcare professional or otherwise) comes into unplanned direct contact with the product, which may or may not lead to the occurrence of an AE.

An occupational exposure will be reported to the drug safety unit within 24 hours of the investigator's awareness, using the SAE report form, regardless of whether there is an associated AE/SAE. Since the information does not pertain to a subject enrolled in the study, the information is not reported on a CRF; however, a copy of the completed SAE report form is maintained in the investigator site file.

8.12. Withdrawal Due to Adverse Events (See Also the Section on Subject Withdrawal)

Withdrawal due to AEs should be distinguished from withdrawal due to other causes, according to the definition of AE noted earlier, and recorded on the appropriate AE CRF page.

When a subject withdraws because of an SAE, the SAE must be reported in accordance with the reporting requirements defined below.

8.13. Eliciting Adverse Event Information

The investigator will report all directly observed AEs and all AEs spontaneously reported by the study subject. In addition, each study subject will be questioned about AEs.

8.14. Reporting Requirements

Each AE will be assessed to determine if it meets the criteria for SAEs. If an SAE occurs, expedited reporting will follow local and international regulations, as appropriate.

8.14.1. Serious Adverse Event Reporting Requirements

If an SAE occurs, Pfizer will be notified within 24 hours of investigator awareness of the event.

If an SAE occurs requiring EAC adjudication, Pfizer will be notified within 24 hours of notification that an SAE has been deemed a nonendpoint and has been sent back to the site. The investigator's SAE awareness date in this instance is identified as the date that the investigator receives the nonendpoint SAE back from the EAC.

As noted in the Protocol-Specified Serious Adverse Events section ([Section 8.6.1](#)), should an investigator judge one of the identified protocol-specified SAEs to have a causal relationship with the investigational product, the investigator must report the event to the sponsor within 24 hours of investigator awareness, even if that event is a component of the endpoint.

In particular, if the SAE is fatal or life-threatening, notification to Pfizer must be made immediately, irrespective of the extent of available AE information. This time frame also applies to additional new information (follow-up) on previously forwarded SAE reports as well as to the initial and follow-up reporting of EDP, exposure via breastfeeding, and occupational exposure cases.

In the rare event that the investigator does not become aware of the occurrence of an SAE immediately (eg, if an outpatient study subject initially seeks treatment elsewhere), the investigator will report the event within 24 hours after learning of it and document the time of his or her first awareness of the AE.

For all SAEs, the investigator is obligated to pursue and provide information to Pfizer in accordance with the time frames for reporting specified above. In addition, an investigator may be requested by Pfizer to obtain specific additional follow-up information in an expedited fashion. This information collected for SAEs is more detailed than that captured on the AE CRF. In general, this will include a description of the AE in sufficient detail to allow for a complete medical assessment of the case and independent determination of possible causality. Information on other possible causes of the event, such as concomitant medications, vaccines, and/or illnesses, must be provided. In the case of a subject death, a summary of available autopsy findings must be submitted as soon as possible to Pfizer or its designated representative.

8.14.2. Nonserious Adverse Event Reporting Requirements

All AEs will be reported on the AE page(s) of the CRF. It should be noted that the form for collection of SAE information is not the same as the AE CRF. Where the same data are collected, the forms must be completed in a consistent manner. For example, the same AE term should be used on both forms. AEs should be reported using concise medical terminology on the CRFs as well as on the form for collection of SAE information.

8.14.3. Medical Device Complaint Reporting Requirements

All medical device complaints, regardless of whether the medical device complaint is associated with an AE, will be collected on the applicable pages within the CRF. This includes potential incidents or malfunctions associated with the use of a medical device product. An incident or malfunction is an event that might have led to death or serious deterioration in health, or if it occurred again might have led to death or serious deterioration in health.

Pfizer will be notified of all medical device complaints within 24 hours of the investigator's awareness of the event.

8.14.4. Sponsor's Reporting Requirements to Regulatory Authorities

AE reporting, including suspected unexpected serious adverse reactions, will be carried out in accordance with applicable local regulations.

9. DATA ANALYSIS/STATISTICAL METHODS

The section outlines statistical considerations and methodologies. Detailed methodology for summary and statistical analyses of the data collected in this study will be documented in a statistical analysis plan (SAP), which will be maintained by the sponsor. This document may modify the plans outlined in the protocol; however, any major modifications of the primary endpoint definition and/or its analysis will also be reflected in a protocol amendment.

The primary comparison is between subjects receiving SA4Ag and subjects receiving placebo.

9.1. Hypotheses and Acceptance Criteria

Vaccine efficacy (VE) is defined as $VE = 1 - RR$, where RR is the relative risk in SA4Ag compared to placebo, ie, the proportion of SA4Ag recipients meeting the primary endpoint relative to the proportion of placebo recipients meeting the primary endpoint. SA4Ag will be compared to placebo testing the hypotheses $H_0: VE \leq 20\%$ vs $H_a: VE > 20\%$.

A conditional power-based⁵⁹ futility procedure will be implemented during case accrual. Periodically the current estimate of VE will be assessed, and there will be a calculation of the power of the study at its planned completion at 48 cases conditional upon that value. The DMC will review the calculation and if the conditional power of the study is low, corresponding to the critical case splits shown in Table 15, futility may be declared and the study may cease enrollment. It is anticipated that this procedure will be implemented after approximately 10 and 15 cases have been accrued, and also at the time of the interim analysis at 24 cases. The assessments after 10 and 15 cases can only result in a possible declaration of futility, not efficacy; as such, there is no impact on the overall alpha level of the study. Full details of the conditional power-based futility procedure will be provided in the SAP.

An interim analysis will be performed after accumulating 24 per-protocol cases for review by the DMC. Only the primary endpoint, defined in [Section 9.3.2](#), will be examined. The probability of the number of vaccine cases will be calculated using the binomial distribution with 24 trials and $p = 0.444$ because, under the null hypothesis and 1:1 randomization, the probability that a selected case is from SA4Ag is 0.444. If the number of vaccine cases is 3 or fewer, then the null hypothesis will be rejected in favor of the vaccine. If significant efficacy is observed at the interim analysis, the study may continue to enroll subjects to ensure that the study will provide sufficient safety data for vaccine licensure.

A 99.7% confidence interval (CI) will be obtained for VE. The confidence level is obtained from the O'Brien-Fleming⁶⁰ alpha levels, explained below. If the study does end for efficacy at interim analysis, events collected subsequent to the interim analysis will be reported in a supplement in a similar manner to that described in Whitehead⁶¹ for overrunning data, described below. Otherwise, the study will continue to the accumulation of 48 cases.

Once 48 per-protocol cases have accumulated SA4Ag will be compared to placebo for the primary endpoint, testing the hypotheses $H_0: VE \leq 20\%$ vs $H_a: VE > 20\%$. SA4Ag will be deemed efficacious if it has 14 cases or fewer out of a total of 48 cases (point estimate of $VE = 58.8\%$ and 2-sided lower 95.1% confidence limit $> 20\%$).

Although the final analysis is expected to have 48 cases, it is possible that additional potential cases will be present in the adjudication system (entered into the adjudication electronic case report form [eCRF]) on the same day that the 48th per-protocol case is reported to the EAC. These additional cases will be included in the final analysis, if confirmed as cases by the EAC. Therefore, the time order of case entry into the adjudication system will determine which cases will be included in the analysis. O'Brien-Fleming boundaries will be maintained for decisions regarding VE. In other words, in the event that more than 48 cases are available for the final analysis, the null hypothesis will be rejected if the lower bound of the 95.1% confidence interval is greater than 20%.

Similarly, although the interim analysis is expected to have 24 cases, it is possible that additional potential cases will be present in the adjudication system (entered into the adjudication eCRF) on the same day that the 24th per-protocol case is reported to the EAC. These additional cases will be included in the interim analysis, if confirmed as cases by the EAC. The time order of case entry into the adjudication system will determine which cases will be included in the interim analysis. O'Brien-Fleming boundaries will be maintained for decisions regarding VE. In other words, in the event that more than 24 cases are available for the interim analysis, the null hypothesis will be rejected if the lower bound of the 99.7% confidence interval is greater than 20%. Even if more than 24 cases are included in the interim analysis, the final analysis will be performed on 48 cases, unless additional cases are available as described in this section. Similar rules for case inclusion will apply to the futility analyses planned at 10 and 15 per-protocol cases.

No multiplicity adjustments will be applied to the secondary endpoints. All other secondary endpoints will be evaluated at a 2-sided alpha level of 0.05.

[figure not shown]
9.2. Sample Size Determination

This sequential analysis uses O'Brien-Fleming limits. Comparing 2 treatments in the number of cases may be restated as a 1-sample test of proportions.⁶² The specifications in the software package EAST (Version 6.4, Cytel Inc, 2016) were 1-sample test on a binomial proportion, 1-sided alpha = 0.025, and an interim analysis, null hypothesis proportion = 0.444 (corresponding to $VE = 20\%$), and alternate hypothesis proportion = 0.230 (corresponding to $VE = 70\%$). The first-stage probability for rejecting the null hypothesis = 0.0015, the first-stage probability for rejecting the alternate hypothesis = 0.2595, and 1-sided probability of rejecting the null hypothesis at the final stage = 0.0245.

One-sided probability = 0.0015 corresponds to a 2-sided confidence level = 99.7%.
One-sided probability = 0.0245 corresponds to a 2-sided confidence level = 95.1%. If power is set to 0.88, then the total would be 48. The interim analysis would be performed after 24 cases have accumulated.

Power is plotted against a range of true efficacy values in Figure 3. These power values are based on the final analysis with 48 cases.

Figure 3. Probability of Rejecting the Null Hypothesis of No Efficacy for a Range of True Efficacy Values at the Final Analysis (48 Cases)

It is anticipated that approximately 6000 subjects may be needed to accumulate 48 per-protocol cases, depending upon the incidence in the placebo group, VE, and dropout rate. For example, if the incidence of cases among placebo recipients is ~1.4% and the VE is 70%, then approximately 6000 individuals would need to be enrolled to detect 48 cases, assuming a dropout rate of 10%. Fewer subjects would need to be enrolled if the incidence of cases is higher among the control group or the VE is less than 80%. For example, if the VE is 60%, under the same assumptions, then approximately 5440 subjects would need to be enrolled to detect 48 cases.

In the event that futility is declared at any point, the study may cease subject enrollment. Vaccinated subjects will continue to be monitored for safety for 6 months after vaccination.

Procedural details for adjusting the sample size will be described in the SAP and/or DMC charter.

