- g. Serum or capillary; fasting value required preoperatively.
- h. Physical examination includes general appearance; musculoskeletal; skin; head, eyes, ears, nose, and throat; heart; lungs; abdominal; neurological; and lymph nodes.
- i. Only applicable for women of childbearing potential. Pregnancy testing may be performed on urine or serum samples.
- j. Record the surgical indication and the planned index surgical procedure. Postoperatively, record the actual index surgical procedure.
- k. Immunogenicity blood draw and colonization swabs must be collected before vaccination at Visit 1 (window: 7 days) and before surgery at Visit 2.
- l. Refer to the respective study visit as detailed in [Section 6](#).
- m. Daily observation for PDIs, AEs, and organ failure events as detailed in [Section 6.3.1.2.1](#).
- n. The e-diary should be collected and AE data reviewed with the subject prior to surgery.
- o. Refer to Appendix 4.

SCHEDULE OF ACTIVITIES FOR ADVERSE AND STUDY EVENT REPORTING

The Schedule of Activities for Adverse and Study Event Reporting table provides an overview of the protocol safety reporting requirements. Refer to the Study Procedures ([Section 6.1](#)) and Assessments ([Section 7](#)) sections of the protocol for detailed information on each procedure and assessment required for compliance with the protocol.

Table 2. Schedule of Activities for Adverse and Study Event Reporting

Visit ID	1	2			3	4	5	6
Protocol Activity	Enrollment and Day of Vaccination	Index Hospital Admission			Day 21 Telephone Contact	Day 42 Postoperative Evaluation	Day 90 Postoperative Evaluation	Day 180 Postoperative Evaluation
		Day of Surgery	Day After Surgery	Day of Discharge				
Study Day	Day -60 to Day -10	Day 1	Day 2	(Day Variable)	Day 21	Day 42	Day 90	Day 180
Visit Window	Day -60 to Day -10	N/A	N/A	N/A	Day 18 to Day 26	Day 35 to Day 49	Day 83 to Day 97	Day 178 to Day 192
Local reactions and systemic events collected in the e-diary	From the day of vaccination for a total of 10 days ^a							
Adverse events	AEs from informed consent to the Day 42 postoperative evaluation							
						Newly diagnosed chronic medical disorders from the Day 42 postoperative evaluation to the Day 180 postoperative evaluation		
Serious adverse events	SAEs from informed consent to the Day 180 postoperative evaluation							
Protocol-defined infection events	PDI events from after surgery to the Day 180 postoperative evaluation							

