2.2.1. Primary Safety Endpoints

- Number and proportion of subjects in each vaccine group with local reactions (redness, swelling, and pain) occurring within the 10-day period following study vaccination.
- Number and proportion of subjects in each vaccine group with systemic events (fever, fatigue, headache, vomiting, diarrhea, muscle or joint pain) occurring within the 10-day period following study vaccination.
- Number and proportion of subjects in each vaccine group with AEs reported during the following time periods:
 - From vaccination until the day of surgery
 - From vaccination until the Day 42 postoperative evaluation
 - From the day of surgery until the Day 42 postoperative evaluation
 - From the Day 42 postoperative evaluation until the day 180 postoperative evaluation (newly diagnosed chronic medical disorders)
- Number and proportion of subjects in each vaccine group with serious adverse events (SAEs) reported during the following time periods:
 - From vaccination until the Day 180 postoperative evaluation
 - From vaccination until the day of surgery

- From the day of surgery until the Day 180 postoperative evaluation

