3. STUDY DESIGN

This is a Phase 2b, multicenter, parallel-group, placebo-controlled, randomized, double-blind study to evaluate SA4Ag safety and efficacy in the prevention of postoperative *S aureus* disease in adults aged 18 to <86 years who are undergoing elective open posterior spinal fusion procedures with multilevel instrumentation.

There are 5 scheduled study visits and 1 scheduled telephone contact during 6 to 8 months of subject participation. Study-eligible subjects who provided consent will be randomized in a 1:1 ratio to receive a single dose of SA4Ag or placebo at Visit 1, which occurs 10 to 60 days prior to undergoing elective open posterior spinal fusion procedures with multilevel instrumentation (*index surgical procedure*). Visit 2 is a longitudinal visit and is to monitor the index hospital admission period from the day of surgery (Day 1) until the day of discharge.

A telephone contact with the subject will occur on Day 21 (window: Days 18 to 26), while postoperative evaluation study visits will occur on Day 42 (window: Days 35 to 49), Day 90 (window: Days 83 to 97), and Day 180 (window: Days 178 to 192) after surgery.

Additional reminders will be communicated to study subjects instructing them to contact the investigational site whenever there is a suspicion of a PDI or a severe postvaccination local reaction or fever.

Unscheduled telephone contacts will be conducted for assessment of severe local reactions, severe fever, and severe systemic events after vaccination. Severe fever and severe local reactions may warrant an unscheduled *severe local reaction or fever assessment visit*.

Following the index hospital admission, unscheduled visits will be conducted for assessment of suspected BSI and/or SSI events, and to assess hospitalization(s) subsequent to the index hospital admission.

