6.5.2. Safety Follow-up

Any vaccinated subject who undergoes the index surgical procedure and who withdraws from the study, and provided the subject is agreeable, will receive safety follow-up as follows:

- AEs will be monitored until the Day 42 postoperative evaluation.
- SAEs will be monitored for at least 6 months after vaccination.

Any vaccinated subject who **does not** undergo the index surgical procedure within 6 months after vaccination or any vaccinated subject who withdraws from the study prior to the index surgical procedure, and provided the subject is agreeable, will receive safety follow-up as follows:

- AEs will be monitored for at least 28 days after vaccination.
- SAEs will be monitored for at least 6 months after vaccination.

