8.2. Reporting Period

For SAEs, the active reporting period to Pfizer or its designated representative begins from the time that the subject provides informed consent, which is obtained prior to the subject's participation in the study, ie, prior to undergoing any study-related procedure and/or receiving investigational product, through Visit 6. SAEs occurring in a subject after the active reporting period has ended should be reported to the sponsor if the investigator becomes aware of them; at a minimum, all SAEs that the investigator believes have at least a reasonable possibility of being related to investigational product will be reported to the sponsor.

AEs will be recorded in the CRF from the signing of the ICD to Visit 4.

Newly diagnosed chronic medical disorders will be recorded in the CRF from Visit 4 to Visit 6.

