### **5.2. Per-Protocol Efficacy Population**

To be included in the PP efficacy population, a subject must:

- meet all eligibility criteria,
- be vaccinated as randomized,
- undergo the index surgery 9 to 90 days (inclusive) after vaccination (this is expanded from 10 to 60 days as stated in the protocol, which represents a more restricted window with the aim of ensuring the per-protocol population timeframe used in the analyses is respected),
- undergo surgery consistent with study-defined criteria for the index surgery,

- not have the index surgery modified to be a staged procedure on separate days,
- have no major protocol violations before reporting of the suspected *S aureus* infection, and
- have no infection or malignancy identified at the index surgical procedure.

Because of confidentiality requirements in Germany, only year of birth can be provided; therefore, the date of birth will be reported as 01 July of the year of birth. Thus, ordinary age calculations might flag a subject as outside the permitted age range of 18 to <86 years. Subjects from Germany who enroll before 01 July and have a calculated age of 17 years may still be included in the PP efficacy population if all other criteria are fulfilled.

Subjects from Germany who enroll after 01 July and have a calculated age of 86 years may still be included in the PP efficacy population if all other criteria are fulfilled.

Subjects will be assigned to the investigational product to which they were randomized (SA4Ag or placebo).

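### After a futility stop, Section 9.2 counts safety follow-up as 6 months from vaccination, which conflicts with a primary safety endpoint that runs to postoperative Day 180

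*Protocol*

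**What the plan says.** On futility, Protocol Section 9.2 gives two sentences: "In the event that futility is declared at any point, the study may cease subject enrollment", and then "Vaccinated subjects will continue to be monitored for safety for 6 months after vaccination". The second is a fixed period counted from vaccination, and it is not worded as a minimum.

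The rest of the plan ends SAE collection at a point counted from surgery:

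- Protocol Section 2.2.1 defines a primary safety endpoint for SAEs over the interval "From vaccination until the Day 180 postoperative evaluation".
- Protocol Table 2 has "SAEs from informed consent to the Day 180 postoperative evaluation".
- Protocol Section 8.2 runs active SAE reporting from consent, before any study procedure or "receiving investigational product, through Visit 6". Visit 6 is the Day 180 evaluation.
- SAP Section 6.2.1 and SAP Table 18 analyse SAEs and deaths to Day 180.

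None of these makes an exception for a futility stop.

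A related rule in Protocol Section 6.5.2 covers subjects who withdraw, if they agree to follow-up: "SAEs will be monitored for at least 6 months after vaccination". That is a minimum.

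Vaccination is at Visit 1, "which occurs 10 to 60 days prior to undergoing elective open posterior spinal fusion procedures with multilevel instrumentation" (Protocol Section 3).

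**The concern.** The same data have two end dates, and the two dates cannot coincide for a subject operated within the protocol window. Section 9.2 is the only sentence that says how long subjects are followed for safety after futility. A site or monitor looking for the post-futility rule would find it there, and could close a subject's safety follow-up before Visit 6 while still complying with the protocol.

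What is at stake is the completeness of a primary safety endpoint. SAEs to Day 180 are affected, and so are newly diagnosed chronic disorders from Day 42 to Day 180. The SAP would not reveal a shortfall. SAP Section 8.1.2 uses the number of subjects in the vaccine group as the denominator for safety proportions, and adjustment for time at risk is planned only for adverse events before surgery (SAP Section 8.1.2.1). The futility branch is also not remote: SAP Section 8.1.3.5 records that the futility criteria were met in December 2018.

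**Working it through.** **Inputs**

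- Days from vaccination to surgery, d: 10 to 60 (Protocol Section 3).
- Day 1 is the day of surgery (Protocol Section 6.3.1.1; SAP Section 6.1), so Day 180 is surgery + 179 days.
- Visit 6 window: Days 178 to 192 (Protocol Section 6.3.5).
- 6 months = 183 days. This is an assumption, varied below from 180 to 184, because the protocol does not convert months to days.

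**1. Reproduce the plan's own figure.** Day 180 falls d + 179 days after vaccination.

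- d = 10: 10 + 179 = 189 days; 189 / 30.44 = 6.2 months.
- d = 60: 60 + 179 = 239 days; 239 / 30.44 = 7.9 months.

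This agrees with the participation of about 6 to 8 months in Protocol Section 3.1. Six months is therefore only the lower end of the planned participation.

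**2. Shortfall if Section 9.2 is read as an end point.** Gap = (d + 179) − 183. The last postoperative day covered is 183 − d + 1.

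| d (days) | Day 180, days after vaccination | Gap (days) | Share of vaccination-to-Day-180 interval | Postoperative day at 6 months |
|---|---|---|---|---|
| 10 | 189 | 6 | 6/189 = 3% | 174 |
| 60 | 239 | 56 | 56/239 = 23% | 124 |

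**3. Sensitivity to the length of 6 months.** With 180 to 184 days, the gap is 9 to 5 days at d = 10 and 59 to 55 days at d = 60.

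**4. Sensitivity to the visit window.** The earliest permitted Visit 6 is Day 178, which is d + 177 days after vaccination. At d = 10 that is 187 days, still 4 days after the 183-day point. The visit window does not close the gap.

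**5. Shortfall if Section 8.2 governs.** SAE reporting continues through Visit 6, and the gap is zero.

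The number of SAEs at issue cannot be computed. The documents give no SAE rate, no distribution of vaccination-to-surgery times, and no count of subjects still in follow-up at a futility stop.

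**The case against.** The strongest reply is that nothing in the plan shortens anyone's visits. The stated consequence of futility is that enrollment may cease. No passage cancels Visit 5 or Visit 6. Section 8.2 is the operative reporting rule, runs through Visit 6 without a futility exception, and asks for later SAEs to be reported if the investigator learns of them. The Section 9.2 sentence sits under sample size, not in a follow-up schedule. Infection surveillance (Section 7.1.1) runs to Day 180 for all operated subjects, and organ-failure surveillance (Section 7.2.3, Table 2) covers hospitalizations over the same period, again without a futility exception. SAP Amendment 5, dated after the futility finding, keeps the Day 180 intervals, and SAP Section 3 plans a supplementary report once all subjects have completed the study.

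Much of this stands. Truncation is one possible reading, not a stated rule. A reader might infer from SAP Section 8.1.3.5 that follow-up was cut short in December 2018, but that section says only that enrollment ceased. Nor is there ground to say that infection or organ-failure surveillance ends early.

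The reply does not remove the conflict. Section 9.2 is the sentence specific to futility, it states a fixed duration, and it lacks the minimum wording that Section 6.5.2 uses. Neither section says which prevails.

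**Conclusion.** There is an internal contradiction that should be fixed. For surgery 10 to 60 days after vaccination, and with 6 months taken as 183 days, Section 9.2 read literally ends safety follow-up 6 to 56 days before the primary safety endpoint does. The gap is zero if Section 8.2 is read as controlling.

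Several stronger readings are tempting, and the documents do not support them:

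- **Follow-up ends at 6 months for withdrawn subjects.** Section 6.5.2 sets a floor for those who agree. It gives operated subjects who withdraw a guaranteed minimum SAE period that is shorter than Day 180, and no more than that. Subjects never operated have no postoperative Day 180 to compare with.
- **The gap reaches 86 days.** This takes surgery at 90 days (90 + 179 − 183 = 86). The 90-day limit comes from the SAP's per-protocol rule, "undergo the index surgery 9 to 90 days (inclusive) after vaccination", which defines an analysis set and does not schedule surgery.
- **The loss falls exactly when the vaccine looks harmful.** Two futility splits do have negative estimated efficacy (7 of 10, −133%; 9 of 15, −50%), but 11 of 24 corresponds to +15.4%. The actual futility finding came at the interim analysis, planned at 24 cases, and its split is not given. A stop for safety is a separate route in Section 9.7.
- **The safety comparison is biased.** The rule is the same in both arms. It threatens the completeness of late SAE data and does not by itself bias the comparison.

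**What to change.** Reconcile Protocol Section 9.2 with Section 2.2.1, Table 2 and Section 8.2, so that safety data collection in operated subjects after a futility stop covers the interval that the primary safety endpoint uses. Confine the vaccination-based wording to subjects who have no postoperative Day 180.

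If a shorter period is kept for any operated subjects, the SAP should report Day 180 SAEs together with actual follow-up time, so that a proportion over the full group is not read as complete.

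The cost is a wording change and, against a literal reading of Section 9.2, up to 56 days (about 8 weeks) more contact per subject operated within the protocol window. Sites may stay open slightly longer after futility. Table 1 (footnote c) and Section 6.3.5 already allow the Day 180 evaluation by telephone if sample collection is arranged.
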